4.5 Secondary Outcomes

4.5.1 Overall Survival

Overall survival, defined as the time from randomization to death, will be summarized by Kaplan-Meier curves for the two treatment groups for the overall study population and stratified by location (West Africa vs. U.S.) and CT value (> 22 vs. \leq 22). Overall survival will be compared between treatment groups using the Cox proportional hazards regression model stratified by location and CT value.

In addition, we will also provide basic summaries of survival at discharge and 58-day survival (N and %) for each group, broken down into the following categories: dead, alive and still in follow- up period.

4.5.2 Time-to-viral load clearance

Time-to-viral load clearance will be summarized by treatment group as follows: mean (SD) for subjects with an observed time-to-viral load clearance, N (%) of patients that died before clearance and N (%) of patients that remain unresolved (i.e. patients that are still being followed). Time-to-viral load clearance will be compared between groups using both the

Wilcoxon and chop-lump test. In both cases, we will order subjects first by time-to-viral load clearance (shortest to longest), followed by subjects that died before clearance (longest to shortest). This treats any death as a worse outcome that than the longest time-to-viral load clearance and will allow us to include all data in a single hypothesis test.

4.5.3 Change in CT value within first 72 hours after randomization

The change in CT value within the first 72 hours will be summarized by treatment group by the mean (SD) and compared using the two-sample t-test. The number and percent of patients that died within 72 hours will also be reported.

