18.2.2 Secondary Endpoints

- 58 day survival time
- Change in Ebola virus threshold cycle within first 72 hours after randomization
- Rate of Ebola viral clearance, quantified as change in threshold cycle per day
- Time from randomization to first negative Ebola PCR
- Cumulative incidence of serious adverse events (SAEs)
- Cumulative incidence of adverse events (AEs) as assessed by laboratory monitoring
- Incidence of infusion related adverse reactions
- Frequency of clinically significant study agent administration or infusion reactions
- Duration from time of symptom onset to discharge from treatment unit or hospital
- Cumulative incidence of progression to severe disease (hemorrhage, multi-organ failure, seizures)
- Cumulative incidence from the time of randomization to resolution of gastrointestinal symptoms (vomiting and diarrhea).

- Cumulative incidence from time of randomization to resolution/progression of individual clinical symptoms
- Maximal serum creatinine in first 14 days
- Pharmacokinetics of investigational therapeutics
- Long term follow-up, when feasible, for any late onset clinical history or symptoms possibly consistent with delayed virologic relapse.

Overview of Study Drugs

By the fall of 2014 preclinical studies, and/or past use of interventions with anecdotal evidence, had identified a number of lead candidate therapeutic interventions that might be considered as prime candidates for further study in patients with known Ebola infection. With time it was thought possible that additional antiviral or immune-enhancing agents with preclinical supporting data may be identified and added to this list. Conversely, emerging toxicity data, failure to replicate previous supportive findings in additional preclinical animal model testing, emerging data from other recent therapeutic trials in West Africa, or similarly negative factors conceivably could also lead to narrowing of this list over time. Further, if inclusion were to be expanded to patients with high-risk exposures but no documented infection, the list of putative MCMs could be broadened even further and would likely include putative vaccine candidates. However, confining this proposed RCT to just enrollees with documented infection, the likely lead candidates initially identified for consideration of study included:

- Convalescent or post-immunization plasma harvested from recent Ebola infection survivors:

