22 STATISTICAL METHODS

Background

A statistically valid plan for conducting a randomized trial of limited and unproven treatment options for Ebola virus disease is not straightforward. Such a trial is unlike most others in several respects: 1) the mortality rate of the "control" arm, i.e., best supportive care arm, is not well known, nor are the factors associated with improved outcome, 2) the oSOC may change as a result of accumulating results from the trial, 3) although the target number of patients is 100/arm, the actual number may be much smaller because the supply of one or more treatments may be severely limited and intermittent, superiority of one arm over another might be established with lesser numbers, and/or the epidemic itself may resolve . However, rather than precluding a randomized controlled trial (RCT), these circumstances favor it, for an

RCT is the most efficient and accurate means of evaluating the benefits of alternative therapies. Nonetheless, an unusual amount of flexibility in trial design is needed to seamlessly accommodate changing circumstances. Flexibility is critical for many reasons. For example, if evidence supports updating the existing oSOC (and dissemination of the new standard is feasible), this change should be implemented seamlessly. If however, the new standard requires a drug with a supply that is nearly depleted (and will remain so for some time), immediate changes to the oSOC may not be possible. Continuation of randomization to the treatment (with the nearly depleted supply) versus the initial standard may be the preferred strategy to allocate the limited supply. Plans for every potential scenario are not possible to specify *a priori*, which leaves such decision making to the domain of the study team in consultation with the DSMB. The present study design attempts to maximize the informational content of the limited data generated, given the above considerations.

Design

The trial will commence with randomization to oSOC (i.e., best supportive care) versus an experimental arm receiving oSOC plus treatment. Randomization will use permuted blocks with variable but small block sizes, and will be stratified by baseline Threshold cycle (CT) value on PCR (≤ 22 versus > 22) and site of treatment (western Africa versus the United States/Europe). The PCR resulted nearest the time of randomization should be used for the stratification.

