3.9.1 Other Secondary Outcomes

In addition to those parameters described in Section 3.6 above, the following will be summarized by treatment group as described:

• Vital Signs: blood pressure, pulse, body temperature, respiratory rate, oxygen saturation – summarized daily by treatment group

• Current symptoms –

Two analyses will be performed to compare the number of symptoms across groups:

- 1. The first analysis of symptoms will compute the average number of symptoms per day during the first 28 days for each patient as well as the average number of days with symptoms. Days with no information on symptoms, including days following the death or discharge of a patient, will be excluded. The groups will be compared using the Wilcoxon rank-sum test. An additional analysis will be conducted using the van Elteren stratified Wilcoxon test on the four strata defined by location (USA/Liberia/Sierra Leone versus Guinea) and cycle threshold (≤22 versus >22).
- The second analysis of symptoms will be identical to the above analysis, but only during the first 3 days. The rationale is that analyses over the entire 28-day period may be difficult to interpret because some patients will be discharged and others may die. Furthermore, the proportion discharged and proportion dying may differ by arm. Restricting attention to the first 3 days will focus the analysis on the initial stage which is free from discharges and some of the deaths.
 - Percent with any symptom
 - Daily summary of number of reported symptoms
 - Summarized for 7 day intervals by treatment group
 - Symptoms at day 28 and day 58 are also summarized.
- Chemistries: measurement of serum creatinine and potassium were required and will be summarized for each 3-day window (i.e. days 1- 3, days 4 6, etc.) by treatment groups, all other chemistries were considered optional and will be summarized as available
 - Additional subgroup analysis will repeat the above for adults and children
 - PCR: blood (note- any CT 40.0 or greater will be treated as negative)
 - \circ summarized for each 3-day window (i.e. days 1- 3, days 4 6, etc.)
 - if more than one PCR is available in a 3 day period for a given subject, the mean result will be used.
 - o summarized as change from baseline for each 3-day window
 - Both of the above will be presented as quantitative (continuous) and qualitative
 - Improvement or worsening of the CT value within the first 72 hours
 - Figure: Kaplan-Meier plot of time to negative Ebola PCR

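### The only test named for the 72-hour CT change is a t-test with no baseline CT adjustment and no place for early deaths; the Final DAP names neither a test nor a rule for deaths

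*Combined protocol and SAP*

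**What the plan says.** **Protocol.** Section 18.2.2 lists "Change in Ebola virus threshold cycle within first 72 hours after randomization" as a secondary endpoint. Section 22 (Design) has randomisation "stratified by baseline Threshold cycle (CT) value on PCR", cut at 22, and by site of treatment.

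**Earlier plan (Data Analysis Plan for MCM RCT).** In section 4.5.3 the change is given for each arm as a mean with its SD and "compared using the two-sample t-test". No covariate or stratum is named. On deaths it says only: "The number and percent of patients that died within 72 hours will also be reported". Neighbouring sections go further. Section 4.5.1 compares overall survival with a "Cox proportional hazards regression model stratified by location and CT value". Section 4.5.2 keeps every patient in one test of viral clearance and explains: "This treats any death as a worse outcome that than the longest time-to-viral load clearance".

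**Final Data Analysis Plan (January 20, 2016).** This updates the earlier plan. Section 3.9.1 lists "Improvement or worsening of the CT value within the first 72 hours" among items to be summarised by treatment group. It gives no test, no adjustment and no rule for deaths. Section 3.9 requires that death be taken into account for viral clearance and discharge. Section 3.8, writing about mortality analyses, calls it biased to leave out patients who die soon after randomisation.

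**The concern.** A patient who dies before any follow-up PCR has no change score. Without a rank, an imputed value or a composite, that patient cannot enter the t-test. If early mortality differs between arms, the patients left in the two groups are no longer those that randomisation made comparable, and a separate count of deaths does not repair the comparison.

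The second issue is precision. Baseline CT is a minimum baseline requirement (protocol 21.4.2.1), and the study team made it a stratification factor because it appeared to be correlated with outcome (amendment B). The test makes no use of it beyond subtraction. With 72 patients randomised, precision matters.

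At stake is the randomised comparison for the objective on immediate viral load kinetics. The primary mortality analysis is not affected.

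**Working it through.** **Stated figure.** The documents give no SD, effect size, power or sample size for this endpoint, so there is nothing to reproduce.

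**Inputs from the documents.** 72 randomised in a 1:1 ratio (Final DAP section 2), taken as 36 per arm. All deaths occurred within 8 days (Final DAP 3.8); the number within 72 hours is not given. One patient fled, and 49 have a discharge time (Final DAP 3.1, 3.9), so deaths number roughly 72 - 1 - 49 = 22. That total is my inference.

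**Assumed inputs.** Early death by 72 hours of 20% v 10% or 30% v 10% (oSOC v ZMapp). These imply 36 x 0.20 + 36 x 0.10 = 10.8 and 36 x 0.30 + 36 x 0.10 = 14.4 early deaths. Both fit within 22, the second at the high end. The correlations below are also assumed. A rise in CT is taken as improvement.

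**1. Precision.** With equal variance at baseline and follow-up and correlation r between them, the change score has variance 2s²(1 - r) and ANCOVA has s²(1 - r²). The ratio is (1 + r)/2:

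| r | 0.3 | 0.5 | 0.7 | 0.9 |
|---|---|---|---|---|
| ANCOVA / change score | 0.65 | 0.75 | 0.85 | 0.95 |

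**2. Selection by death, closed form.** Let q0 and q1 be the shares dead by 72 hours on oSOC and ZMapp, and rho the correlation between propensity to survive and CT change. With no true CT effect, the difference among survivors (ZMapp minus oSOC), in SDs of CT change, is rho x [L(q1) - L(q0)], where L(q) = phi(z_q)/(1 - q).

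L(0.10) = 0.1755/0.90 = 0.195; L(0.20) = 0.2800/0.80 = 0.350; L(0.30) = 0.3477/0.70 = 0.497.

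| oSOC v ZMapp | bracket | rho = -0.3 | 0 | 0.3 | 0.5 | 0.8 |
|---|---|---|---|---|---|---|
| 20% v 10% | -0.155 | +0.05 | 0 | -0.05 | -0.08 | -0.12 |
| 30% v 10% | -0.302 | +0.09 | 0 | -0.09 | -0.15 | -0.24 |

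**3. Simulation.** 36 per arm, 2,500 runs per scenario, no true CT effect, two-sided 0.05 (2.5% expected on each side). Ranges cover r = 0.5 and 0.8. Biases are in SDs of CT change.

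| Early death depends on | oSOC v ZMapp | t-test bias | ANCOVA bias | t-test favours oSOC / ZMapp | worst-rank test favours ZMapp |
|---|---|---|---|---|---|
| baseline CT only | 20% v 10% | +0.04 to +0.06 | about 0 | 1.2-1.6% / 3.7-3.8% | 13-15% |
| CT change only | 20% v 10% | -0.08 to -0.12 | -0.08 to -0.09 | 5.1-7.2% / 1.0-1.1% | 6-7% |
| both | 20% v 10% | -0.03 to -0.05 | -0.07 to -0.09 | 3.0-3.8% / 1.1-2.0% | 8-9% |
| baseline CT only | 30% v 10% | +0.07 to +0.11 | about 0 | 0.7-1.0% / 4.4-5.6% | 39-42% |
| CT change only | 30% v 10% | -0.17 to -0.21 | -0.15 to -0.17 | 9.3-12.8% / 0.2-0.5% | 12-16% |
| both | 30% v 10% | -0.06 to -0.11 | -0.13 to -0.17 | 3.6-6.5% / 0.6-1.0% | 21-25% |

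The sign turns on why patients die early. If death follows low baseline CT alone, regression to the mean pushes the t-test towards ZMapp, and ANCOVA removes the bias. If death follows the CT change itself, the t-test leans towards oSOC and ANCOVA does not cure it. Where both act, ANCOVA shows the larger bias of the two.

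**4. Cost of a worst-rank test.** In a further simulation (1,500 trials, 36 per arm, early death tied to a poorer CT course, 15% early death in both arms, true gain of 1.5 cycles), power was 66% for the t-test, 70% with baseline adjustment and 41% for the worst-rank test. These depend on the assumed link between death and CT course, so only their order should be relied on.

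**The case against.** The strongest reply is that the t-test belongs to a plan for DSMB reports that has since been updated. The Final DAP governs publication, and there the item is one descriptive line under other secondary outcomes. The virologic analysis that carries weight, time to viral clearance, already ranks deaths worst and has a version stratified by location and CT. All of that is correct, and it limits the importance of this point. It would be wrong to call the 72-hour change the main antiviral endpoint: section 1 of the earlier plan and section 3.9 of the Final DAP both put viral clearance ahead of it. What remains is that the protocol lists the endpoint and the operative plan says neither how to compare it nor what to do with early deaths.

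A reader might infer three stronger things that the documents do not support.

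- *That the test is restricted to patients alive at 72 hours.* This is not written. It is the natural reading, since the dead receive no value, but a patient who died on Day 3 could contribute an earlier PCR; the minimum schedule, though its table is broken, appears to include one on Day 2.
- *That the analysis is biased against ZMapp.* This needs ZMapp to reduce early death and the patients so saved to have smaller CT rises. The documents report a link between baseline CT and outcome, and under that link alone the bias runs the other way.
- *That baseline CT is ignored.* A change score subtracts it. What is missing is covariate adjustment, which under randomisation costs precision and is not in itself a bias.

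The remedies can also be criticised. ANCOVA still leaves out patients without a follow-up CT, and a worst-rank test partly re-tests mortality. Both points stand and shape the fix. PCR sampling was also sparse on many days (Final DAP 3.9), so usable numbers may be below the 36 per arm assumed here.

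**Conclusion.** The concern holds as a gap in specification with two distinct consequences.

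First, the only named test leaves precision unused. The ANCOVA variance would be 0.65 to 0.95 of the change-score variance for r between 0.3 and 0.9, a saving of 5% to 35%.

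Second, early deaths have no place in the comparison. If early mortality differs by arm, the resulting bias is roughly -0.2 to +0.1 SD of CT change, with either sign possible; at worst among the cases tried, the t-test wrongly favoured oSOC in 12.8% of runs against a nominal 2.5%. If early mortality is equal and the same mechanism acts in both arms, this bias vanishes.

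The early-death rates, rho and r are all assumptions. The structural finding does not rest on them: there is no adjustment in the earlier plan, and no test and no rule for deaths in the Final DAP.

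**What to change.** Write the analysis into Final DAP 3.9.1; changing section 4.5.3 of the earlier plan alone would not reach the operative document.

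1. Compare 72-hour CT between arms by ANCOVA on treatment and baseline CT. State that it applies to patients with a follow-up CT, define which measurement counts, and report by arm how many lack one and how many of those died. This is a free improvement: baseline CT is already collected, and the cost is a sentence of wording. It should not be presented as removing selection by death.
2. Add, as a supportive analysis, a rank test that places deaths before 72 hours worst, following section 4.5.2 of the earlier plan. Label it a combined death and CT outcome. Say beside it that it loses power if early deaths are equal between arms, and that it partly re-tests mortality if they are not: with no CT effect at all, it favoured ZMapp in 6% to 42% of simulated runs when ZMapp reduced early death.

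The rank test accompanies the ANCOVA and does not replace it. Neither needs new data.

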4.5.4 Daily Outcomes

The following will be summarized by treatment group as described:

- Vital Signs: blood pressure, pulse, body temperature, respiratory rate, oxygen saturation summarized daily by treatment group
- Summary of optimized supportive care provided: electrolytes and intravenous fluids, other treatments (ventilation, ECMO, supplemental oxygen, etc.) – summarized daily by treatment group
- Current symptoms summarized daily by treatment group
- Chemistries: creatinine and potassium are required and will be summarized for each 3- day window (i.e. days 1- 3, days 4 – 6, etc.) by treatment groups, all other chemistries are optional and will be summarized as available
- PCR: summarized for each 3-day window (i.e. days 1- 3, days 4 6, etc.) by treatment groups
- Hematology and coagulation: optional data summarized as available
- Urinalysis: optional data summarized as available
- Imaging and resuscitation: optional data summarized as available

Summaries for continuous-valued outcomes by treatment group will include N and mean, SD or median, IQR. Summaries for categorical outcomes will include N and %.

4.6 Safety outcomes

4.6.1 SAEs

SAEs will be summarized and compared between treatment groups as follows:

- Number and percent of patients experiencing SAEs by treatment group. Test of statistical significance will use Fisher's exact test.
- Counts of SAEs by treatment group. The rate of SAEs will be formally compared using a zero-inflated negative binomial model.
- Kaplan-Meier cumulative event curves by treatment group; p-values will be provided for comparing the active treatment groups to placebo using the log-rank test

• For SAEs that are assessed as related to study drug, counts by treatment groups and p- value from zero-inflated negative binomial model.

4.6.2 Safety listings

Line listings by treatment group will be provided for SAEs and "unanticipated problems". Listings will include the SID, treatment group label, diagnosis, relatedness to treatment, date of onset, time from treatment to onset, event status (recovered/resolved, recovering/resolving, not recovered/not resolved, recovered/resolved with sequelae, death), date of resolution or death, and EVD status.

4.6.3 Pregnancies

The number of pregnancies reported during the 58-day follow-up period after randomization, and the outcomes of these pregnancies, will be summarized by treatment group.

4.6.4 Infusion Reactions

The number and percent of patients experiencing infusion reactions will be summarized for patients randomized to ZMapp. 95% CIs for the rate of infusion reactions will also be provided. Infusion reactions will also be broken down by the specific infusion reactions reported on the ZMapp infusion form and summarized by the number and percent experiencing each infusion reaction.

4.6.5 Infusion Interruptions

The number and percent of patients for which infusion interruptions occurred will be summarized for patients randomized to ZMapp. 95% CIs for the rate of infusion interruptions will also be provided.

4.6.6 Unanticipated problems

Incidence of "unanticipated problems" will be tabulated for each of the treatment groups. Reports will have similar format as the summary reports for SAEs.

5 DAILY STUDY PROGRESS REPORTS ON THE WEB

Progress reports include reports on accrual, baseline characteristics, and data completeness. These data summaries are pooled across study groups. The reports are similar to those described in the open report section.

These reports will be available on the study web site (controlled access), updated daily. Additional reports may be provided to study leadership on request.

6 SAE REPORTS TO LEAFBIO

Listings for SAEs that are assessed as related to the studied treatment will be provided to LeafBio. Reports will be as described in the protocol.

7 SHELLS FOR TABLES AND FIGURES

Shells for key tables and figures are provided in this section. For example, a shell for Kaplan- Meier curves for the primary endpoint is shown; similar Kaplan-Meier curves will also be provided for several secondary endpoints, as described earlier.

Final Data Analysis Plan for PREVAIL II Ebola Virus Disease Medical Countermeasures (EVD MCM) Trial

January 20, 2016

Table of Contents

1	Introduction	19
2	Study Overview	19
3	PLANNED Analyses	20

	3.9.4 LATE CLINICAL SYMPTOMS	

1 Introduction

This document describes the content proposed for the primary statistical analysis of PREVAIL II, the randomized controlled trial of ZMapp in acute Ebola virus disease (EVD). The focus is on analyses that address the major randomized comparisons for key safety, tolerability and efficacy outcome measures, including those needed to address the study's primary objective as well as the main secondary objectives. This analysis plan therefore includes the key analyses for presentation or publication of the primary conclusions of the study.

2 Study Overview

The study protocol is a master protocol for the evaluation of multiple candidate countermeasures for the treatment of EVD. Given the waning epidemic, the initial (and, to date, only) phase of the trial was focused only on the evaluation of ZMapp, although the study was designed to provide flexibility to introduce additional treatments under certain situations that are described in the protocol. The Primary Objective of this study was to establish the safety and efficacy of ZMapp in patients diagnosed with Ebola virus infection.

Patients were randomized in the United States, Liberia, Sierra Leone, and Guinea in a 1:1 allocation ratio to optimized standard of care (oSOC) versus oSOC plus ZMapp. A maximum of 200 subjects were to be randomized (100 per treatment arm) in this trial. The primary endpoint for the trial is survival as assessed at Day 28.

Following the first randomized patient on March 13, 2015, the Data and Safety Monitoring Board (DSMB) reviewed interim data on 7 occasions. Following each review, the DSMB indicated that they had no safety concerns and recommended the study continue. In anticipation of study closure due to the absence of EVD, pooled (both treatment groups combined and blinded) outcome data were provided to the U.S. study team by the unblinded statisticians, [name] and [name], on November 25, 2015. These data were used to update the data analysis plan that was prepared prior to the beginning of the trial. The pooled data were updated on December 31, 2015 following submission of 28 day follow-up data for the last person randomized on November 21, 2015.

On January 8, 2016, a provisional draft of the updated data analysis plan was shared with the Food and Drug Administration, Mapp Biopharmaceutical, INSERM, and other participating site investigators. The final data analysis plan detailed in the present document considers the comments that were received concerning that January 8th proposal. The document retains some of the information from the original analysis plan concerning the format and content of open and closed DSMB reports.

As of January 14, 2016, 42 days after the last case of EVD in Liberia was discharged, all three countries in West Africa had been declared Ebola-free. Accordingly, the study was planned for closure to new accrual as of that date. Subsequent to that determination there has been a potential resurgence of EVD reported in Sierra Leone; the scope and duration of that recent outbreak, as well as whether any potential new cases may be referred for enrollment, are unclear at this time. If additional enrollments do occur, this will delay the timeline for implementing the final study analysis as summarized in this document. As of the original

planned date of closure on 1-14-2016 there have been a total of 72 patients randomized on the protocol.

3 PLANNED Analyses

Unless otherwise stated, all tables, figures, and listings will show results by randomized arms. For tables with categorical variables, the number (%) will be presented. For tables with continuous variables, the mean, standard deviation, median, 25th and 75th percentiles, min and max will be presented. The number with missing values will also be shown. In calculation of percentages, subjects with missing data will not be included in the denominator. Data presented as listings or figures will be specifically noted.

